8.2 Disease-free Survival

A primary endpoint is Disease-Free Survival (DFS), as defined in Section 6.2. The 95% confidence interval for DFS observed on 150 fully followed patients will have half-width of 8% or less; that is, it will be the observed DFS rate plus or minus 8%. This figure is conservative in that the width will be less for DFS rates far from 50%. It is slightly anticonservative in the presence of loss to follow-up.

The DFS estimate and its confidence interval will be compared to similar statistics observed for patients treated with standard care fractionation schedules such as those presented in [Zelefsky et al. High dose rate radiotherapy delivered by intensity modulated conformal radiotherapy improves the outcome of localized prostate cancer, J. Urol. 166: 876, 2001]. In addition, efficacy in these data will be modeled with the linear-quadratic formula [Chappell, R., Nondahl, D., and Fowler, J.F. Modeling dose and local control in radiotherapy. Journal of the American Statistical Association. Vol. 90 (1995), pp. 829-838] to examine the hypothesis, which underlies the logic of fractionation, that prostate cancers have an alpha/beta ratio which makes them better able to repair radiation injury than surrounding late responding tissues.

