1.0 BACKGROUND

1.1 Introduction

[figure not shown]
Prostate cancer is the most common non-skin cancer in American men, resulting in over 30,000 deaths annually in this country. Optimal treatment for localized, potentially curable, prostate cancer has not been determined, but radiation therapy has an established and major role in the management of localized disease, a role supported by evidence that disease control rates comparable to radical prostatectomy are achieved but with less toxicity.

The probability of achieving biochemical control after radiation therapy is related to the pre-treatment PSA, tumor grade and local stage, with PSA and grade being the most important factors. For example, patients with pre-treatment PSAs of less than 6 ng/ml and Gleason scores less than or equal to 6, have 5-year biochemical control rates of 87%, whereas patients with PSAs 10 – 20 ng/ml and Gleason scores of 7 have control rates of only 45%. Radical prostatectomy outcomes are also influenced strongly by these same pre-treatment predictors.

It has long been felt that one of the most important factors limiting the success of radiation therapy has been the inability to deliver adequate radiation dose without producing unacceptable toxicity. More recently, however, innovations in cancer imaging, radiation treatment planning and treatment delivery technology have created opportunities for safe dose escalation.

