3.0 SELECTION OF PATIENTS

- Histologically proven adenocarcinoma of the prostate.
- Stage ≤ T2b disease, as defined by 1997 AJCC classification
- Predicted risk of lymph node involvement (by standard nomograms) of 15% or less (24), OR histologically negative pelvic nodes
- Gleason score ≤ 7
- No evidence of distant metastasis
- Age 18+
- Informed consent signed in accordance with institutional protocol
- Pretreatment evaluations must be completed as specified in Section 7.0.
- ECOG performance status 0-1
- No previous or concurrent cancers, other than localized basal cell or squamous cell skin carcinoma, unless continually disease free for at least 5 years
- No prior pelvic irradiation, prostate brachytherapy, or bilateral orchiectomy
- Gonadotropin-releasing hormone agonist (GnRH-a) use permitted (maximum of 6 months duration). Anti-androgen therapy permitted concurrently with GnRH-a.
- No previous or concurrent cytotoxic chemotherapy
- No radical surgery or cryosurgery for prostate cancer
- The absence of any co-morbid medical condition which would constitute a contraindication for radical radiotherapy
- The absence of serious concurrent illness of psychological, familial, sociological, geographical or other concomitant conditions which do not permit adequate follow-up and compliance with the study protocol.
- No current use of anticoagulation therapy, other than aspirin.

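### Section 8.2 compares DFS with published series and specifies no control for PSA or Gleason mix, an error source that the stated 8% half-width does not cover

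*Combined protocol and SAP*

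**What the plan says.** Section 8.2 makes DFS a primary endpoint and gives its precision: "The 95% confidence interval for DFS observed on 150 fully followed patients will have half-width of 8% or less". It adds: "This figure is conservative in that the width will be less for DFS rates far from 50"%. The planned use is then: "The DFS estimate and its confidence interval will be compared to similar statistics observed for patients treated with standard care fractionation schedules". One published series is cited as an example. No risk grouping, matching, standardisation, covariate adjustment or decision rule is attached to this comparison. The linear-quadratic modelling in the same section addresses the alpha/beta ratio, and the text does not say that it corrects the comparison for risk group.

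Section 1.1 describes the predictors of biochemical control, "with PSA and grade being the most important factors". Its examples are men with PSA below 6 ng/ml, for whom the text reads "Gleason scores less than or equal to 6, have 5-year biochemical control rates of 87"%, and men with PSA 10–20 ng/ml, for whom it reads "Gleason scores of 7 have control rates of only 45"%.

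Section 3.0 admits "Gleason score ≤ 7" and stage T2b or lower. It sets no explicit PSA limit; a nodal-risk limit of 15%, or histologically negative nodes, restricts PSA only indirectly. Section 8.3 adjusts for pretreatment PSA and grade, but only in the biomarker Cox model, and takes 15% as the average five-year failure rate.

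**The concern.** An overall DFS is a weighted average over risk groups, with weights set by whoever happens to enrol. If the trial and a published series have different proportions of favourable and intermediate men, their overall rates will differ even when control within each risk group is identical. The confidence interval in section 8.2 does not allow for this, because it measures only chance variation in 150 men.

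This is the only comparison of efficacy with outside data that the document sets out. Taken at face value, a higher DFS could be credited to hypofractionation when it reflects a more favourable intake, or a real gain could be hidden by a less favourable one. The plan recognises the problem in section 8.3, where PSA and grade are adjusted for in an exploratory analysis. It does not carry the same protection to the primary-endpoint comparison.

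**Working it through.** **Inputs.** n = 150 and a half-width of 8% or less (section 8.2); control of 87% and 45% in two example subgroups (section 1.1); 15% average five-year failure, so DFS of about 85% (section 8.3). The 30- and 20-point contrasts below are assumptions, used to show a range.

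**1. The plan's own figure.** Half-width = 1.96 × √(p(1 − p)/n).
- At p = 0.50: 1.96 × √(0.25/150) = 8.0 points. The stated figure is reproduced.
- At p = 0.85: 1.96 × √(0.1275/150) = 5.7 points.

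**2. Effect of mix.** Suppose there are two risk groups with the same control rates in the trial and in the published series. Then

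difference in overall DFS = (difference in favourable share) × (contrast between groups).

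With the section 1.1 examples the contrast is 87 − 45 = 42 points. A 10-point difference in favourable share then moves overall DFS by 0.10 × 42 = 4.2 points.

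**3. Shift in favourable share that equals the half-width** (half-width ÷ contrast), in percentage points:

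| Contrast between groups | To reach 8.0 points | To reach 5.7 points |
|---|---|---|
| 42 (section 1.1 examples) | 19 | 14 |
| 30 (assumed) | 27 | 19 |
| 20 (assumed) | 40 | 29 |

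**4. Which row is plausible?** At 87% and 45%, an overall DFS of 85% needs a favourable share of (85 − 45)/42 = 95%. So if section 8.3 is right about failure, either the intake is expected to be almost wholly favourable or the contrast in this setting is smaller than 42 points. The first row is therefore an upper illustration.

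**5. Illustration at that upper contrast.** Take 70% favourable men in the trial and 50% in the reference (both assumed), with no true difference within groups. Trial DFS is 0.70 × 87 + 0.30 × 45 = 74.4%. Reference DFS is 0.50 × 87 + 0.50 × 45 = 66.0%. The gap is 8.4 points. Summing exact binomial probabilities over 0 to 150 disease-free men, the trial's 95% interval (formula in step 1) lies wholly above 66.0%, treated as fixed, with probability 0.66.

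**6. Precision within groups.** With an assumed 75 men in a group:
- 1.96 × √(0.1275/75) = 8.1 points at DFS 85%;
- 1.96 × √(0.25/75) = 11.3 points at DFS 50%.

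With the 95/5 split of step 4, the smaller group has about 7 of 150 men. At 45% its half-width is 1.96 × √(0.2475/7), about 37 points.

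**The case against.** The best case for the plan has four parts.

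- **The 42-point contrast is not the trial's contrast.** Section 1.1 offers the two rates as examples. They are opposite corners of the PSA and Gleason range, with men in between left out, and no dose is given for them. Section 1.2 links poor control in intermediate and higher risk men to conventional doses and reports better results at higher doses, so the gap may be narrower here. The nodal-risk limit may also exclude some men with PSA 10–20 and Gleason 7; how many cannot be determined, because the nomogram is not shown. This stands, and it is why a range is given.
- **Silence is not exclusion.** The wording about similar statistics leaves room for like-for-like risk groups. A reader might infer that the plan rules out or disregards PSA and Gleason; the text shows only that it does not specify their use. That is still a gap in a primary-endpoint analysis, because strata and comparators chosen after results are seen permit selective comparison.
- **Nothing is decided by this comparison.** Section 8.2 gives no test, margin or decision rule, and toxicity governs escalation and further accrual (sections 5.2, 5.3 and 8.1). This stands and limits the consequence to interpretation of the efficacy result.
- **The remedy may be weak.** If nearly all men are favourable, the other stratum will be too small to inform, and the published series may not report matching strata. This stands as a limit on the fix. Standardisation would not rescue a very small stratum either.

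**Conclusion.** The concern holds in a limited form. As written, section 8.2 leaves the comparison with published series open to case-mix bias, on factors that the protocol itself ranks first and adjusts for elsewhere. The 8% half-width is correctly calculated for what it measures, and that does not include differences in mix.

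The shift in favourable share that would equal the half-width runs from about 14 to 40 percentage points, depending on the contrast (42 to 20 points) and on whether the half-width is 5.7 or 8.0 points. This rests on a two-group simplification with equal within-group control in trial and reference. Smaller contrasts would need larger shifts, and below an 8-point contrast no shift in mix reaches 8 points.

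A reader might infer that a 19-point imbalance is the expected threshold, or that the comparison will in fact be biased by more than its interval. The documents support neither reading: 19 points belongs to the extreme example contrast, it sits uneasily with the 15% failure rate in section 8.3, and neither the trial's nor the comparator's mix is given. What they support is that case mix can matter on the scale of the stated precision and that the plan specifies nothing to control it. The point should be addressed, but no trial decision is invalidated by it.

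**What to change.** Amend section 8.2 to do the following:

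- Define PSA/Gleason risk groups in advance, using the pre-study PSA (section 7.3) and the Gleason score needed for eligibility (section 3.0), and estimate DFS with a confidence interval in each.
- Compare each group with the matching stratum of the published series, where that series reports one.
- Where the series reports only its risk mix, standardise: weight the trial's group-specific DFS by the published shares and give the interval for that weighted estimate.
- Present the unadjusted overall comparison as descriptive, and state precision per group beside the overall 8%.

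No extra patients, visits or data items are needed, and the efficacy analysis already waits for a median of five years of follow-up (section 6.1). The cost is wider intervals within groups, depending on the split accrued: 8.1 to 11.3 points with an assumed 75 men, and much wider if a group is small. The method also relies on what the published series report. If a series gives neither strata nor mix, the plan should say that the comparison with it cannot be adjusted.

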8.3 Correlation of Biomarkers with Clinical Outcome

The percent labeling observed immunohistochemically with each biomarker studied will ultimately be analyzed for correlations with clinical outcome once sufficient clinical follow-up is achieved (median follow-up of at least 5 years. Three markers (p53, bcl-2, and Ki-67) will be analyzed for prognostic significance using a Cox proportional hazards regression analysis accounting for each of the 250 patients' follow-ups, and adjusting for pretreatment PSA and tumor grade. For purposes of power calculations only, we will assume that marker scores will be divided at their medians and modeled as binary covariates, so that prevalences are by definition 50%. Also, we compute power using binary failure/no-failure five year outcomes; these produce conservative (slightly too small) estimates of power. We invoke the usual two-sided test of significance at the conducted .05 level, divided by three using a Bonferroni adjustment to avoid bias due to multiple comparisons.

Suppose that the relative risk induced by positive markers is 3. This, by the proportional hazards assumption, implies five-year failure rates of approximately 22% vs. 8% which average to 15%, a failure rate consistent with that reported in a patient population such as this treated with dose-escalated radiotherapy. Then by the above assumptions the power to detect each marker's effect, after adjusting for multiple comparisons, is approximately 79%. This is reasonable for an exploratory study. Should failure rates be higher than the assumed 15%, then the power would be greater.

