2.0 OBJECTIVES

2.1 To evaluate acute and long-term tolerances to dose-per-fraction escalation in the treatment of prostate cancer using optimized treatment delivery that employs IMRT, daily rectal balloon displacement, and transabdominal ultrasound localization of the prostate.

2.2 To clinically evaluate local tumor control and biochemical progression-free survival and metastasis-free survival.

2.3 To immunohistochemically measure the levels of p53, Bcl-2, and Ki-67 in pre-treatment diagnostic biopsy specimens from patients enrolled on this study and will analyze correlations between these markers and clinical outcomes (freedom from biochemical and metastatic failure) in univariate and multivariate fashion, taking conventional prognosticators such as stage, grade and PSA into account.

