4.0 REGISTRATION PROCEDURES

Patients can be registered only after eligibility criteria are met. Patients must have signed informed consent. Patients are registered prior to any protocol treatment by faxing the registration page to [contact] and calling [contact]. The UW data managers will verify eligibility, assign a case number, dose level, and confirm the number of fractions per week.

Patients will be enrolled on the highest available dose level open to accrual. If the highest dose level has reached full accrual with insufficient follow-up for further dose-per-fraction escalation, accrual will take place at one dose level lower, if one exists.

Enrollment will be permanently closed when the maximum tolerated dose per fraction is reached or when the dose per fraction escalation is complete.

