The accrual intervals for each level stem directly from the escalation rules that will be followed, which are described in detail in Section 8. While not shown, predicted tumor control at each of the levels can be extrapolated from the fitted model of actual tumor control data in Figure 1, combined with the increased biologically effective doses calculated for each dose-per fraction-level as shown in the last column of Table 1. Such calculations are theoretical, but provide the rationale to believe that the hypofractionation schemas proposed here may produce increasingly better tumor control with fewer fractions.

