6.3 Progressive Disease

Any patient with rising PSA on 3 successive serum measurements will be considered to have recurrent or progressive disease. The date of failure will be taken as midway between the nadir PSA date and the date of the first of the three rising PSAs.

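### The biomarker Cox model in Section 8.3 leaves out stage, which the objectives promise, pools dose levels expected to differ in tumor control, and makes no provision for GnRH-agonist use

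*Combined protocol and SAP*

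**What the plan says.** - **Model (8.3).** Three markers are tested by Cox regression in 250 patients, "adjusting for pretreatment PSA and tumor grade". Each test is two-sided at 0.05/3. Stated power is about 79% for a relative risk of 3, with five-year failure of 22% against 8%. The section calls the study exploratory.
- **Objective (2.3, also 1.4).** The marker analysis is to be done "taking conventional prognosticators such as stage, grade and PSA into account". Stage is named here but not in 8.3.
- **Dose level (4.0, 5.2).** At registration the data managers "assign a case number, dose level, and confirm the number of fractions per week". Table 1 gives equivalent doses of 82.6, 85.1 and 85.5 Gy for Levels I to III. Section 5.2 ties predicted tumor control to "the increased biologically effective doses calculated for each dose-per fraction-level".
- **Hormone therapy (3.0).** "Gonadotropin-releasing hormone agonist (GnRH-a) use permitted (maximum of 6 months duration"), with anti-androgen allowed alongside it.
- **Failure (6.2, 6.3).** Disease-free status depends heavily on PSA nadir and trend, and "Any patient with rising PSA on 3 successive serum measurements will be considered to have recurrent or progressive disease". Neither section makes any provision for hormone exposure.
- **Data items (7.3, 9.0).** Neither the evaluation table nor the data list names GnRH-agonist use, dates or duration.

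**The concern.** The stated model does not deliver what the objective promises, because stage is missing. It also treats patients from three schedules as sharing one baseline hazard, although the rationale for the trial is that tumor control should rise with dose per fraction. Finally, a treatment left to choice, and plausibly related to the PSA-based outcome, is ignored. If GnRH agonists are given more often to men at higher perceived risk, and the markers track risk, part of any marker effect could reflect hormone use, or be masked by it. Section 1.5 wants markers that predict response to radiation, so this mixing would bear on the interpretation. Outcomes are about seven years away (5.9), so settling the model now also avoids choosing covariates after the data are seen.

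**Working it through.** **1. Reproduce the plan's power.** Inputs from 8.3: n = 125 per marker group (250 split at the median), p1 = 0.22, p0 = 0.08, two-sided alpha 0.05/3, so z = 2.394.

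Arcsine formula: power = Φ(h·√(n/2) − z), with h = 2·asin√p1 − 2·asin√p0.

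h = 0.4029; 0.4029 × √62.5 = 3.185; Φ(3.185 − 2.394) = **78.6%**, matching the stated 79%. The rates imply a hazard ratio of ln(0.78)/ln(0.92) = 2.98, matching the stated 3. The stated power includes no covariates.

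**2. Dose level.** Equivalent dose in 2 Gy fractions at α/β = 1.5 is D(1 + d/1.5)/(1 + 2/1.5). This gives 82.1, 85.1 and 85.5 Gy, close to Table 1, so the expected contrast is mainly Level I against the other two.

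- Assume a failure hazard ratio of 0.8 for Levels II/III against I, and a sizeable imbalance: 25% of marker-positive and 15% of marker-negative men at Level I. Bias factor: (0.25 + 0.75 × 0.8)/(0.15 + 0.85 × 0.8) = 0.85/0.83 = 1.02.
- A simulated population with level independent of the marker (hazard ratio 0.8 or 1 per level), GnRH use of 30% in both marker groups (hazard ratio 0.5 or 0.7) and true marker ratio 3 gives 2.97 to 2.99 when both factors are omitted.

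**3. GnRH use associated with the marker.** The documents give no prevalence, effect or association, so all inputs are assumptions: use of 40% in marker-positive and 20% in marker-negative men, GnRH hazard ratio g of 0.5 or 0.7.

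Bias factor = (1 − 0.4 + 0.4g)/(1 − 0.2 + 0.2g). Power uses the formula in step 1, with mean failure held at 15%.

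| g | Bias factor | Apparent ratio | Failure rates | Power |
|---|---|---|---|---|
| 0.5 | 0.80/0.90 = 0.889 | 2.67 | 21.4% v 8.6% | 69% |
| 0.7 | 0.88/0.94 = 0.936 | 2.81 | 21.7% v 8.3% | 74% |

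The reverse imbalance (20% against 40%) inflates the ratio to 3 × 1.125 = 3.38 or 3 × 1.068 = 3.20. Simulation agrees: 2.63 to 2.80 one way, 3.19 to 3.36 the other.

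**4. Null marker.** The same imbalance gives a spurious ratio, in either direction, of 1.125 (g = 0.5) or 1.068 (g = 0.7). At 1.125 the rates are 15.8% and 14.2%, h = 0.0455 and h·√62.5 = 0.360. The false-positive rate is Φ(0.360 − 2.394) + Φ(−0.360 − 2.394) = 0.021 + 0.003 = **2.4%**. At 1.068 it is 1.9%. The nominal rate is 1.7%.

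**5. Price of adjusting.** Expected failures: 250 × 0.15 = 37.5. With marker, PSA and grade as single terms there are 37.5/3 = 12.5 failures per coefficient; adding stage and GnRH use gives 37.5/5 = 7.5. By the events formula (Schoenfeld), power at ratio 3 is 83.4% with no correlation between the marker and the added terms. It is 81.2%, 78.7% and 73.1% if they explain 5%, 10% and 20% of the marker's variance. The 40%/20% imbalance corresponds to 0.2² × 0.25/(0.3 × 0.7) = 4.8%. On this scale, ignoring that imbalance gives 72% to 78%, against about 81% after adjusting for it.

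**The case against.** The strongest reply is that this is an exploratory analysis with few events, so a short covariate list is a reasonable choice, and that the wording in 2.3 is an open list of examples. Tissue is optional (1.5), so 250 patients and 37 failures are likely upper figures. PSA and grade are already in the model and would absorb part of any link between GnRH use and risk. All of this stands and limits the weight of the point. It does not explain why stage, named in the objective, is absent from the model.

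Several stronger readings are tempting but not supported:

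- **That dose level confounds the marker effect.** Markers are measured on pre-treatment biopsies, and level depends on what is open at registration. The documents show no route from marker to level beyond chance or drift in case mix.
- **That sequential enrolment biases the result through unequal follow-up.** Censoring in the Cox model handles unequal follow-up, and 4.0, 5.1 and 8.1 let accrual return to a lower level.
- **That GnRH use is already recorded.** Section 3.0 only permits it. The eligibility checklist and toxicity sheet are not in the supplied text, so capture can be neither confirmed nor ruled out.
- **That false positives could triple.** A rate near 5.7% needs a spurious ratio of about 1.3. At a GnRH hazard ratio of 0.5 that takes roughly 60% against 18% use (0.91/0.70 = 1.3), which nothing in the documents suggests.

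**Conclusion.** The point holds as a modest, worthwhile correction. The stage mismatch between 8.3 and Sections 1.4 and 2.3 is plain from the text and needs no assumption. Pooling dose levels under one baseline hazard is an avoidable assumption, at odds with the plan's own prediction, but its likely cost is some precision and not material bias.

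The GnRH part is conditional: there is almost no bias if use is unrelated to the marker. The losses in steps 3 and 4 require an assumed association and an assumed effect on a PSA-based outcome; the documents supply neither. The stated 79% is not an arithmetic error.

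**What to change.** In 8.3:

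1. Add stage to PSA and grade, as 2.3 promises. Stage is already needed for eligibility.
2. Stratify the Cox model by dose level, which is assigned at registration. Separate baseline hazards add no coefficients.
3. Include GnRH-agonist use (yes/no) as a covariate or a prespecified sensitivity analysis. First confirm that the case forms capture it, and add the item if they do not.
4. State that the 79% is an unadjusted figure.

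Items 1, 2 and 4 are wording changes. Item 3 may also need a data item, and retrieval for men already enrolled. The statistical cost is one or two more coefficients on at most about 37 expected failures. If that is judged too many, keep stage and the stratification in the main model and make GnRH use the sensitivity analysis.

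### Section 8.3: Holm's step-down rule would hold the same 5% family-wise error as the planned Bonferroni rule and never declare fewer markers, a small to moderate gain at almost no cost

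*Combined protocol and SAP*

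**What the plan says.** Section 8.3 states that "Three markers (p53, bcl-2, and Ki-67) will be analyzed for prognostic significance using a Cox proportional hazards regression analysis", with adjustment for pretreatment PSA and tumor grade. The multiplicity rule is a "two-sided test of significance at the conducted .05 level, divided by three using a Bonferroni adjustment to avoid bias due to multiple comparisons". No other multiplicity rule appears in the plan, and no reason is given for choosing the single-step form.

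For power, 8.3 uses 250 patients and assumes that "marker scores will be divided at their medians and modeled as binary covariates, so that prevalences are by definition 50"%. The effect is set by "Suppose that the relative risk induced by positive markers is 3", which "implies five-year failure rates of approximately 22% vs. 8% which average to 15"%. On that basis "the power to detect each marker's effect, after adjusting for multiple comparisons, is approximately 79"%, which the section accepts as adequate for exploratory work. The plan asks for no simultaneous confidence intervals for the three markers.

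**The concern.** Under single-step Bonferroni each marker must reach p ≤ 0.0167 whatever the other two show. Once one marker has been declared at that level, the 5% family-wise limit no longer requires so strict a threshold for the others. Holm's procedure uses this: the smallest p-value is compared with 0.05/3, the next with 0.05/2 and the last with 0.05, stopping at the first failure.

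The analysis is short of information. A 15% failure rate in 250 men gives 0.15 × 250 = 37.5 failures. Section 5.9 puts the correlative analysis about seven years away, and section 1.5 makes tissue participation optional, so fewer than 250 men may contribute. At stake is whether a second or third prognostic marker is reported as negative when the same error rate would have allowed it to be declared.

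**Working it through.** **Inputs from 8.3.** Three markers; two-sided 0.05/3 = 0.01667 (critical z = 2.394); 250 patients split at the median, so 125 per group; failure rates 22% and 8%. The correlation between the marker tests is not given, so I take 0 and 0.3 as assumptions.

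**The plan's figure.** Arcsine formula: h = 2·asin√0.22 − 2·asin√0.08 = 0.9764 − 0.5735 = 0.4029. Power = Φ(h·√(125/2) − 2.394) = Φ(3.185 − 2.394) = Φ(0.791) = 78.6%. The unpooled normal formula gives 77.8%. The stated 79% is reproduced.

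**Why Holm cannot lose.** Its first threshold is Bonferroni's and the later ones are looser, so every marker that Bonferroni declares is also declared by Holm. For the error rate, suppose m of the three markers are truly null. The first false declaration can occur only at a step whose threshold is at most 0.05/m. It therefore needs some null p-value ≤ 0.05/m, and the chance of that is at most m × 0.05/m = 5% under any dependence.

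**Size of the gain, independent tests.** Set power per marker at 79%, so the z-statistic of a real marker has mean 2.394 + 0.806 = 3.200. Its p-value then falls:
- at or below 0.0167 with probability A = 0.790;
- at or below 0.025 with probability Φ(3.200 − 2.241) = 0.8312, so the band 0.0167 to 0.025 has B = 0.0412;
- at or below 0.05 with probability Φ(3.200 − 1.960) = 0.8926, so the band 0.025 to 0.05 has C = 0.0614.

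For a null marker the same bands have probabilities 0.0167, 0.0083 and 0.025.

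Under Holm a marker in band A is always declared. In band B it is declared if at least one other marker is in band A. In band C it is declared if both others are at or below 0.025 and at least one of them is in band A. Hence, per real marker:
- One real: 0.790 + 0.0412 × (1 − 0.9833²) + 0.0614 × (0.025² − 0.0083²) = 0.790 + 0.0014 + 0.00003 = 79.1%.
- Two real: 0.790 + 0.0412 × (1 − 0.21 × 0.9833) + 0.0614 × (0.8312 × 0.025 − 0.0412 × 0.0083) = 0.790 + 0.0327 + 0.0013 = 82.4%.
- Three real: 0.790 + 0.0412 × (1 − 0.21²) + 0.0614 × (0.8312² − 0.0412²) = 0.790 + 0.0394 + 0.0423 = 87.2%.

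The chance of declaring all three real markers goes from A³ = 49.3% to A³ + 3A²B + 3A²C + 3AB² + 6ABC = 0.4930 + 0.0772 + 0.1149 + 0.0040 + 0.0120 = 70.1%. The chance of declaring at least one is the same under both rules, because both need the smallest p-value to be ≤ 0.0167.

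**How often a p-value between 0.0167 and 0.05 is recovered.** Divide each gain by B + C = 0.1026: 0.0014/0.1026 = 1.4% with one real marker, 0.0340/0.1026 = 33% with two, 0.0817/0.1026 = 80% with three.

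**Error actually used.** With all three markers null, 1 − (1 − 0.0167)³ = 4.9% under both rules. With two real and one null, the false-positive chance is 1.7% under Bonferroni and 0.0167 + 0.0083 × 0.9559 + 0.025 × 0.6892 = 4.2% under Holm. Both are inside 5%.

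**Sensitivity.** With correlation 0.3 between the tests, simulation gives 86.3% per marker when all three are real. Starting from the pooled two-proportion test instead (76.4% per marker), simulation with independent tests gives 76.6%, 80.0% and 85.1% for one, two and three real markers. The levels shift but the pattern is the same.

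**The case against.** The strongest reply is that nothing here is wrong. Bonferroni is valid, the power figure is sound, and the analysis is exploratory and for research only. Choosing between two valid procedures could be called a matter of taste. This stands as far as severity goes: the point is an improvement and cannot be rated higher.

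It could also be said that the Bonferroni sentence is only a power-planning assumption, since it sits among such assumptions. That is weak. The restriction to power calculations is attached to the median split, and the sentence is the plan's only multiplicity rule.

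Three stronger readings are tempting, and the documents do not support them.
- A reader might infer that any marker with p between 0.0167 and 0.05 is lost under the plan and recovered by Holm. With p-values of 0.03, 0.04 and 0.20, Holm declares nothing.
- A reader might infer that the plan expects several markers to matter, which would make the larger gains the likely ones. Section 5.9 calls the apoptotic markers promising and says Ki-67 could be of special interest for hypofractionation. Those are reasons to study them; they do not predict that two or three will each be prognostic after adjustment. The relative risk of 3 in 8.3 is a supposition for the power calculation.
- A reader might infer that Bonferroni buys nothing. It does give simple confidence intervals that match its decisions. The plan does not ask for such intervals, so the benefit is small here, but it exists.

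**Conclusion.** The point holds as an efficiency gain. The planned rule is valid and 79% power per marker stands. Holm keeps the same 5% family-wise limit, never declares fewer markers, and adds about 0.1, 3 or 8 points of power per real marker when one, two or three markers are real. The 8 becomes about 7 at a correlation of 0.3. These sizes assume 79% power for each real marker and the stated correlations; the ordering of the two procedures needs no such assumption.

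The rise from 49% to 70% in the chance of finding all three should not be quoted alone, because it requires all three markers to carry the full assumed effect at once. If only one marker is prognostic, the change is negligible. Holm also spends more of the permitted error when real and null markers are mixed, though never more than 5%.

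**What to change.** In 8.3, before any marker outcome is analysed, replace the Bonferroni rule with Holm's: take the three Cox p-values adjusted for PSA and grade, one per marker and all for the same named outcome; order them; compare them in turn with 0.05/3, 0.05/2 and 0.05; stop at the first that is not significant. State that 79% is the minimum power per marker, since the first step is the Bonferroni threshold.

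The outcome has to be named because 8.3 does not name it, while objective 2.3 lists both biochemical and metastatic failure, in univariate and multivariate analyses. That gap affects Bonferroni and Holm equally.

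The cost is a sentence or two, with no extra patients, tissue or data. Confidence intervals that match stepwise decisions are less simple; Bonferroni intervals can still be shown beside the Holm decisions.
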